Rescreening may be allowed for subjects who failed initial screening. Only 1 rescreening will be allowed (see [Section 5.1](#) and [Section 5.2](#)). If a subject is rescreened for the study, the subject must sign a new informed consent and will be issued a new subject number. Informed consent for a rescreened subject must be obtained prior to performing any study-related assessments or collecting any data for the Screening visit.

Treatment period

On Day 1, eligible subjects will enter an open-label treatment period to receive ligelizumab 120 mg sc q4w. The first dose of study drug will be administered on Day 1 (Visit 110). The last dose of ligelizumab 120 mg will be administered on Day 337 (Week 48, Visit 230) study visit.

Approximately 65 subjects will be allocated to the ligelizumab 120 mg q4w arm. Subjects are expected to attend all site visits based on the assessment schedule ([Table 8-1](#)).

Post-treatment follow-up period

The post-treatment follow-up period is 12 weeks with the last follow-up visit (Visit 1999) corresponding to 16 weeks after the last treatment dose. No investigational treatment will be given during the post-treatment follow-up period. Subjects will be allowed to take their rescue medication on an as needed basis, assessed on a daily basis by the subjects. Subjects will be required to visit the study center every 4 weeks during the post-treatment follow-up period.

Patients will be eligible for post-trial access after completion of the study.

4 Rationale

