2.7.1.1 Crude and Exposure-Adjusted Incidence Rate

The crude incidence rate is defined as the percentage of subjects with a specific adverse event divided by the total number of subjects.

Due to expected differences in exposure and follow-up due to varied duration of study participation between participants, adverse event incidence rates will be provided as “exposure adjusted AE incidence rates (EAIRs)” in addition to the crude incidence.

The EAIR is defined as the number of subjects with a specific event divided by the total exposure-time among the subjects in the study group. That is, the EAIR is calculated as:

$EAIR = n / \sum t_i$, where n is the number of subjects having the i^{th} type event, and t_i is a subject's exposure time and defined as the shortest of the following:

- 1) time to the first episode of the i^{th} type event (if the event occurs),
- 2) duration of study treatment plus the 16-week washout period (approximately corresponding to five half-lives) after last treatment dose, or
- 3) end of the analysis period (week 64 for all safety follow-up).

The total exposure time of all subjects in a treatment group is $\sum t_i$. The EAIR is interpreted as the number of events occurring in a population per unit time. The exact Poisson 95% confidence interval for the EAIR will be provided as well, where an exact $100*(1-\alpha)\%$ confidence interval will be derived as follows (Garwood 1936, Sahai and Khurshid 1993):

- Lower confidence limit $L = \frac{0.5C_{\alpha/2,2n}}{\sum t_i}$ for $n>0$, 0 otherwise,
- Upper confidence limit $U = \frac{0.5C_{1-\alpha/2,2n+2}}{\sum t_i}$,

where $C_{\alpha,k}$ is the α th quantile of the Chi-square distribution with k degrees of freedom.

Whenever applicable, exposure adjusted incidence rates will be provided for the type as below:

1. TEAE and TESAE: Primary SOC level, PT level
2. TEAE of special interest

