2.7.1.2 Adverse events of special interest / grouping of AEs

Refer to the AEs analyses described in [Section 2.5](#) in this document.

Adverse events of special interest

The following adverse events of special interest (AESI) will be summarized separately by each category and SOC/PT.

Details will be provided in the separate document (eCRS). The search criteria in the latest eCRS corresponding the MedDRA version at the database lock will be used and reported in the CSR.

- Hypersensitivity reactions (including anaphylaxis)
- Cardiovascular and Cerebrovascular (CCV) events
- Neoplastic conditions
- Injection site reactions
- Serum Sickness
- Eosinophilic Conditions / Churg-Strauss Syndrome

- Parasitic (Helminthic) infections
- Thrombocytopenia

Injection site reactions

For injection site reactions (ISR), besides the overall summary table for AESI, ISR will be summarized by events and subject separately in each treatment group for the following categorical variables.

The ISR selected by eCRS as ISR will be mapped to the exposure dosing window. The PTs (possible more than 1 records) happened during the same dosing window (on or after the drug injection administration date and before the next injection administration), they will be considered as one ISR event. If there is any missing dose injection occurred, any selected event will be all considered related to the last drug administration happened. For example, if a dose administration scheduled dose at Week 4 happened, and the next dose administration happened at Week 12 with Week 8 dose administration missing, all injection site reaction happened on or after Week 4 drug administration date before Week 12 drug administration date will be considered related to Week 4 drug administration.

If there were multiple PTs occurred during one dosing window, the worst case will be used for the summary and analysis of ISR. If there is any PT record detailed information (e.g. severity, resolution time, action or outcome etc..) missing or unknown, this PT record will not be included for the particular category summary of ISR. If all PT records for one ISR are with unknown/missing information for the summary category, the ISR will be summarized in the unknown category in the table.

- Recurrence of ISR (single ISR, 2-3 ISRs, > 3 ISRs)
- Severity of ISR (best to worst cases: mild, moderate, severe)
- Timing of ISR (during first administration, Week 4-Week 8, Week 8-Week 24, After Week 24)

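### The exposure-adjusted rate for injection site reactions counts about 12 injection-free weeks per event-free subject, which puts it about 16% to 19% below a treatment-period rate

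*SAP*

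**What the plan says.** SAP 2.7.1.1 divides the number of subjects with an event by summed exposure time. Each subject's time is the shortest of three quantities:

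- "time to the first episode of the" event type in question, if it occurs;
- "duration of study treatment plus the 16-week washout period (approximately corresponding to five half-lives) after last treatment dose";
- the end of the analysis period, set at Week 64.

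Exact Poisson 95% limits use the same denominator. Where applicable, the rates are given for all TEAEs and serious TEAEs by SOC and preferred term, and for each "TEAE of special interest". The list in SAP 2.7.1.2 includes "Injection site reactions", and neither section gives them a separate person-time rule.

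For the other ISR summaries, SAP 2.7.1.2 ties reactions to injections: "The ISR selected by eCRS as ISR will be mapped to the exposure dosing window". A window runs from one injection to the next, and no end is stated for the window after the last one.

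Protocol Section 3 puts the last dose at Day 337 (Week 48) and says of the 12 weeks from Week 52: "No investigational treatment will be given during the post-treatment follow-up period".

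**The concern.** The 16 weeks are justified by half-life, that is, by how long drug remains in the body. That suits systemic events. An ISR is a local response to an injection, and a new one is not plausible months after the last injection. Event-free subjects, who supply most of the person-time, nevertheless keep adding time until Week 64.

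The effect goes one way: it lowers the rate and both confidence limits. Safety is the primary objective, and ISRs are the one exception that Protocol 4.5 names to its statement that no dose-dependent signal is apparent. SAP 2.7.1.1 introduces the adjustment because exposure will vary between subjects. For ISRs it adjusts for a mixture of injected time and untreated follow-up.

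**Working it through.** **Inputs from the documents**
- Planned sample size: 65 (Protocol 12.8.1, SAP 3.1).
- Injections every 4 weeks at 13 visits, the last at Week 48 (Protocol 3 and 6.6.1).
- Exposure duration: last dose minus first dose plus 28 days (SAP 2.4.1). Protocol 12.5.2 also ends the treatment phase for adverse events 4 weeks after the last dose.
- TEAE window: 16 weeks after the last dose (SAP 2.5.1).
- Dropout: 10% (SAP 3.1).

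**Assumptions.** The documents give no ISR rate for this trial. I take 3 to 19 of 65 subjects (5% to 29%). The ends lie close to the placebo (5.2%) and high-dose (28.6%) figures of the asthma study in Protocol 4.5. Mean first onset at Week 4 to 24 has no source in the documents.

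**The plan's own figure.** 48 + 16 = Week 64, which matches the stated cap. The treatment-period alternative ends at 48 + 4 = Week 52.

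**One event-free completer.** 64 weeks against 52. The planned rate is lower by 12/64 = 18.75%. Put the other way, the treatment-period rate is 64/52 = 1.23 times the planned one.

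**Whole study, no dropout.** With n ISR subjects at mean onset week t:

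- planned person-time D64 = (65 − n) × 64 + n × t
- treatment-period person-time D52 = (65 − n) × 52 + n × t
- planned rate ÷ treatment-period rate = D52/D64

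| n | t | D64 (weeks) | D52 (weeks) | D52/D64 | Planned rate lower by |
|---|---|---|---|---|---|
| 3 | 4 | 3,980 | 3,236 | 0.813 | 18.7% |
| 6 | 12 | 3,848 | 3,140 | 0.816 | 18.4% |
| 19 | 24 | 3,400 | 2,848 | 0.838 | 16.2% |

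With 52.18 weeks per year, the middle row gives 6 × 100 × 52.18/3,848 = 8.1 per 100 patient-years as planned, against 6 × 100 × 52.18/3,140 = 10.0.

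**With 10% dropout.** Let last doses of early stoppers be spread evenly over Weeks 0 to 44 (mean 22). Event-free early stoppers then average 22 + 16 = 38 weeks as planned, against 22 + 4 = 26. For an ISR share p and mean onset at Week 8, the mean time per subject is 8p + (1 − p)(0.9 × 64 + 0.1 × 38) as planned, against 8p + (1 − p)(0.9 × 52 + 0.1 × 26).

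- p = 12.5% (8 subjects): 54.7 against 44.2 weeks, or 68.2 against 55.1 patient-years. The rate is 11.7 (95% limits 5.1 to 23.1) against 14.5 (6.3 to 28.6) per 100 patient-years.
- p = 28.6% (19 subjects): 57.5 against 46.8 patient-years. The rate is 33.1 (19.9 to 51.6) against 40.6 (24.4 to 63.4).

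For p from 12.5% to 28.6% and mean onset from about Week 0 to Week 26, the reduction is 16.7% to 19.5%. If treatment duration in the second item already includes 28 days, the upper end is 20.1%.

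**Where the figure is smaller.** Without dropout, a 28.6% share with mean onset at Week 40 gives 15.0%, and a 50% share with mean onset at Week 26 gives 13.3%.

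**Dependence on the last dose.** SAP 5.1 lists a Week 52 dosing date among the dates that can end treatment. With an injection at Week 52, an event-free completer would have 56 of 64 weeks within 28 days of an injection, and the reduction would be 8/64 = 12.5%.

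**The case against.** The 28-day comparator is a convention. If an ISR needs a recent injection, much of each 4-week interval is also time with little risk. The SAP's resolution categories run from 24 hours to more than 72 hours. With an assumed 7-day window, a completer would have 13 × 7 = 91 days at risk and not 364. The SAP also leaves the window after the last injection open. This stands: 16% to 19% is the distance between two ways of counting time. A reader might infer that the documents exclude any ISR risk in Weeks 52 to 64; they do not say so.

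A reader might also see a mismatch between numerator and denominator. There is none: TEAEs are counted to 16 weeks after the last dose and so is person-time. Shortening only the denominator would create a mismatch. Injection-site preferred terms also appear in the SOC and preferred-term EAIR tables, so a change to one row gives the same events two rates.

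A further tempting step is that the ISR rate could not be compared with other ligelizumab studies. The documents say only that Japanese data will be evaluated together. They do not give the other studies' EAIR rule; if it is also 16 weeks, a change here alone could reduce comparability.

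Finally, ISRs have other summaries that the extra weeks do not touch: crude incidence, the tables by dosing window, and Kaplan-Meier for time to first reaction. The trial is single-arm and descriptive, and no decision rule depends on this rate. All of this limits the importance of the point, but none of it removes the dilution of the planned rate.

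**Conclusion.** The point holds as a dilution. Against a treatment-period rate ending 28 days after the last dose, the planned ISR EAIR and its exact Poisson limits are about 16% to 19% lower, under the assumed ISR share and onset. For completers the maximum is 18.75%; a value near a fifth needs early stoppers. Late onset or a high ISR share makes it smaller. The direction is always towards a lower rate.

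The result rests on a last injection at Week 48 and on 28 days as the reference window, which the documents use for exposure and for treatment-phase events but not expressly for ISRs. The SAP summarises treatment-period TEAEs separately but specifies no treatment-period EAIR, so the report would hold no person-time rate for ISRs that is free of the untreated follow-up.

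**What to change.** In SAP 2.7.1.1, add a rule for the ISR category of special interest. A subject's time ends at the earliest of first ISR, last injection plus 28 days, or end of observation. Only ISRs with onset in that window enter the numerator, and any later ones are listed. Alternatively, report ISRs per 100 injections, using the dosing-window mapping already in SAP 2.7.1.2.

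Keep the 16-week rule for the other events of special interest and for the SOC and preferred-term tables. Add a footnote there that injection-site rows use the longer denominator.

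Reconcile the Week 52 dosing date in SAP 5.1 with the protocol's last dose at Week 48.

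The cost is a few sentences and one further derivation from data already collected. The report will carry two denominators, and the ISR rate will look slightly less favourable.

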2.7.1.2 Adverse events of special interest / grouping of AEs

Refer to the AEs analyses described in [Section 2.5](#) in this document.

Adverse events of special interest

The following adverse events of special interest (AESI) will be summarized separately by each category and SOC/PT.

Details will be provided in the separate document (eCRS). The search criteria in the latest eCRS corresponding the MedDRA version at the database lock will be used and reported in the CSR.

- Hypersensitivity reactions (including anaphylaxis)
- Cardiovascular and Cerebrovascular (CCV) events
- Neoplastic conditions
- Injection site reactions
- Serum Sickness
- Eosinophilic Conditions / Churg-Strauss Syndrome

- Parasitic (Helminthic) infections
- Thrombocytopenia

Injection site reactions

For injection site reactions (ISR), besides the overall summary table for AESI, ISR will be summarized by events and subject separately in each treatment group for the following categorical variables.

The ISR selected by eCRS as ISR will be mapped to the exposure dosing window. The PTs (possible more than 1 records) happened during the same dosing window (on or after the drug injection administration date and before the next injection administration), they will be considered as one ISR event. If there is any missing dose injection occurred, any selected event will be all considered related to the last drug administration happened. For example, if a dose administration scheduled dose at Week 4 happened, and the next dose administration happened at Week 12 with Week 8 dose administration missing, all injection site reaction happened on or after Week 4 drug administration date before Week 12 drug administration date will be considered related to Week 4 drug administration.

If there were multiple PTs occurred during one dosing window, the worst case will be used for the summary and analysis of ISR. If there is any PT record detailed information (e.g. severity, resolution time, action or outcome etc..) missing or unknown, this PT record will not be included for the particular category summary of ISR. If all PT records for one ISR are with unknown/missing information for the summary category, the ISR will be summarized in the unknown category in the table.

- Recurrence of ISR (single ISR, 2-3 ISRs, > 3 ISRs)
- Severity of ISR (best to worst cases: mild, moderate, severe)
- Timing of ISR (during first administration, Week 4-Week 8, Week 8-Week 24, After Week 24)
- Time to resolution (best to worst cases: 24 hours, 24-48 hours, 48-72 hours, > 72 hours)
- Action taken (best to worst cases: Dose not changed, drug interrupted, drug withdrawn)
- Outcome (best to worst cases: Recovered/resolved, recovered/resolved with sequelae, not recovered/not resolved, Fatal)

Furthermore, for time to first treatment emergent injection site reaction, the Kaplan-Meier estimator will be used to estimate the cumulative incidence function for the entire study.

Adjudicated AEs

From the AESIs listed above, the following AEs will be adjudicated by the independent committee. The adjudicated events will be listed, and a summary table will be provided following the adjudication.

- Anaphylaxis
- Cardiovascular and Cerebrovascular (CCV) events

- Neoplastic conditions (Malignancy)

COVID-19 infection related analyses

A listing and summary of all TEAE COVID infections will be presented. All suspected and confirmed infection will be provided. The COVID-19 infection will be filtered based on eCRS.

Liver toxicity

Separate summary table and listing will be provided for the liver toxicity related adverse event.

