10.1 Definition of adverse events and reporting requirements

10.1.1 Adverse events

An adverse event (AE) is any untoward medical occurrence (e.g., any unfavorable and unintended sign [including abnormal laboratory findings], symptom or disease) in a subject or clinical investigation subject after providing written informed consent for participation in the study. Therefore, an AE may or may not be temporally or causally associated with the use of a medicinal (investigational) product.

The investigator has the responsibility for managing the safety of individual subject and identifying adverse events.

Novartis qualified medical personnel will be readily available to advise on trial related medical questions or problems.

The occurrence of adverse events must be sought by non-directive questioning of the subject at each visit during the study. Adverse events also may be detected when they are volunteered by the subject during or between visits or through physical examination findings, laboratory test findings, or other assessments.

Adverse events must be recorded in the appropriate CRF under the signs, symptoms or diagnosis associated with them, accompanied by the following information (as far as possible) (if the event is serious refer to [Section 10.1.2](#)):

1. The Common Toxicity Criteria (CTC) AE grade (version 5 or higher);
2. its relationship to the study treatment and other investigational treatment. If the event is due to lack of efficacy or progression of underlying illness (i.e. progression of the study indication) the assessment of causality will usually be 'Not suspected'. The rationale for this guidance is that the symptoms of a lack of efficacy or progression of underlying illness are not caused by the trial drug, they happen in spite of its administration and/or both lack of efficacy and progression of underlying disease can only be evaluated meaningfully by an analysis of cohorts, not on a single subject;
3. its duration (start and end dates) or if the event is ongoing, an outcome of not recovered/not resolved must be reported;
4. whether it constitutes a SAE (see [Section 10.1.2](#) for definition of SAE) and which seriousness criteria have been met;
5. action taken regarding with study treatment.

All adverse events must be treated appropriately. Treatment may include one or more of the following:

- Dose not changed

- Dose reduced/increased
- Drug interrupted/withdrawn

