2.1.1 General definitions

Study day and Study week based on eDiary

Study day is defined as the number of days since the date of first dose of study medication. The date of first dose of study medication is defined as Day 1 and the day before the first dose of study medication is defined as Day -1.

Therefore, for a particular date, study day will be calculated as follows:

- for dates on or after the first date of study medication,
Study day = Assessment date – Date of first dose of study medication + 1;
- for dates prior to the first date of study medication,
Study day = Assessment date – Date of first dose of study medication.

For event dates on or after Day 1, study day for a particular event date will be calculated as [Date of event] - [Date of first dose] + 1. For the dates before Day 1, study day for an event date will be calculated as [Date of event] - [Date of first dose].

Duration of an event will be calculated as (Event end date - Event start date + 1).

The study weeks are defined based on the study days starting with Day 1 (see [Table 2-1](#)), which is the day the patient receives the first study treatment.

The study week defined in this section will be used for the efficacy analyses based on the eDiary.

Table 2-1 Study Week definition based on Study Day of eDiary

Study Week	Study Days
Baseline	(-7)-(-1)
1	1-7
2	8-14
x	$7 \times (x-1) + 1 - 7 \times x$
64	442 – 448

For the by visit summary tables, they will include all the information collected at the scheduled visit. The unscheduled visit information will not be included in the by visit summary table. No remapping visit will be provided.

Study Week based on RaveX collected visit information

For the by visit summary tables (lab results, ECGs, vital signs, PROs, [REDACTED] etc..) , all the information collected at the scheduled visit will be included for the analyses. Unscheduled visit information will not be included in the by visit summary descriptive statistics. The unscheduled visit information will be only included in the maximum or minimum post treatment assessment summaries.

Baseline

In general, baseline is defined as the last measurement (including unscheduled visits) prior to or on the first dose of study drug at Day 1. Refer to the baseline definitions for each analysis described in the later sections.

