2.5.2 Statistical hypothesis, model, and method of analysis

The number of subjects who had a treatment emergent adverse event (events which started on or after the first dose of study treatment and within 16 weeks after the last study treatment, or events present prior to the first dose of study treatment but increased in severity based on preferred term within 16 weeks after the last study treatment) will be summarized overall, by system organ class (SOC) and preferred term descriptively. No statistical model will be applied for the primary endpoints.

All information obtained on adverse events will be displayed by subject.

All treatment emergent adverse events (TEAEs) during treatment period will also be summarized separately.

In addition to what is described in the primary endpoints section, treatment emergent adverse events with the number and percentage of patients having any adverse event overall, by system organ class and preferred term will be provided for:

- Serious treatment emergent adverse events (TESAEs)
- TEAEs by maximum severity
- TEAEs suspected by the investigator as study drug related
- TEAEs leading to permanent discontinuation of study drug

The number of subjects with TEAEs of special interest will be listed and summarized.

A subject with multiple adverse events within a primary system organ class is only counted once towards the total of the primary system organ class.

Unless otherwise specified, primary system organ classes will be sorted alphabetically and, within each primary system organ class, the preferred terms will be sorted in descending order of frequency. If a patient reported more than one adverse event with the same preferred term, the adverse event will be counted only once. If a patient reported more than one adverse event within the same primary system organ class, the patient will be counted only once at the system organ class level.

In addition, the most frequent TEAEs will be presented by preferred term in descending order of frequency.

For TEAEs by maximum severity, missing severity will be assumed to be severe in the summary table.

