5.2.2 AE date imputation

Rules for imputing the AE end date:

- If the AE end date month is missing, then the imputed end date should be set to the earliest of the study end date, 31DECYYYY or date of death.
- If the AE end date day is missing, then the imputed end date should be set to the earliest of the study end date, last day of the month or date of death.
- If AE year is missing or AE is ongoing, then the end date will not be imputed.

Rules for imputing the AE start date:

- If imputing end dates, then this should be done prior to calculating imputed start dates.

The following table explains the notation used in the logic matrix. Please note that **missing start dates** will not be imputed.

	Day	Month	Year
Partial Adverse Event Start Date	Not used	MON	YYYY
Treatment Start Date	Not used	TRTM	TRTY

The following matrix explains the logic behind the imputation.

	MON MISSING	MON < TRTM	MON = TRTM	MON > TRTM
YYYY MISSING	(1) No convention			
YYYY < TRTY	(a) Before Treatment Start	(b) Before Treatment Start	(b) Before Treatment Start	(b) Before Treatment Start
YYYY = TRTY	(a) Uncertain	(b) Before Treatment Start	(c) Uncertain	(c) After Treatment Start
YYYY > TRTY	(a) After Treatment Start	(b) After Treatment Start	(b) After Treatment Start	(b) After Treatment Start

Before imputing AE start date, find the AE start reference date.

1. If the (imputed) AE end date is complete and the (imputed) AE end date < treatment start date, then AE start reference date = min(informed consent date, earliest visit date).
2. Otherwise, AE start reference date = treatment start date.

Impute AE start date:

1. If the AE start date year value is missing, then the date uncertainty is too high to impute a rational date. Therefore, if the AE year value is missing, then the imputed AE start date is set to NULL.
2. If the AE start date year value is less than the treatment start date year value, then the AE started before treatment. Therefore:
 - a. If AE month is missing, then the imputed AE start date is set to the mid-year point (01JulYYYY).
 - b. Otherwise, if AE month is not missing, then the imputed AE start date is set to the mid-month point (15MONYYYY).
3. If the AE start date year value is greater than the treatment start date year value, then the AE started after treatment. Therefore:
 - a. If the AE month is missing, then the imputed AE start date is set to the year start point (01JanYYYY).

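### For injection-site-reaction resolution time, SAP 2.7.1.2 leaves an ongoing preferred term out of the worst-case choice, so a partly unresolved reaction can be tabulated as '24 hours'

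*SAP*

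**What the plan says.** - **One event per window.** SAP 2.7.1.2 groups all ISR PTs that fall between one injection and the next: "they will be considered as one ISR event". With several PTs in a window, the worst case is reported.
- **Missing details.** Where there is any "PT record detailed information (e.g. severity, resolution time, action or outcome etc..) missing or unknown, this PT record will not be included" in the summary of that item. The record stays in the other ISR summaries. If every record of an ISR lacks the item, the ISR goes to an 'unknown' row.
- **Resolution scale.** "Time to resolution (best to worst cases: 24 hours, 24-48 hours, 48-72 hours, > 72 hours". There is no level for a reaction that has not resolved.
- **Outcome scale.** The same section has an Outcome summary that includes a not recovered/not resolved level, ranked worse than either recovered level.
- **End dates.** SAP 5.2.2: "If AE year is missing or AE is ongoing, then the end date will not be imputed". End dates lacking only the day or month are imputed late.
- **Duration.** SAP 2.1.1: "Duration of an event will be calculated as (Event end date - Event start date + 1"). Without an end date there is no duration.
- **Data collected.** Protocol 10.1.1 asks for "its duration (start and end dates) or if the event is ongoing", an outcome of not recovered/not resolved.

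**The concern.** The SAP chooses the worst case within a dosing window, but a record that has been left out cannot be the worst. For resolution time, the record most likely to lack a value is the one that has not resolved. Erythema that clears the same day alongside induration that persists would be reported with the erythema's time. The worst-case principle then gives the best case, and the Outcome table contradicts the resolution table for the same reaction.

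The information is not absent. The onset date, the not-recovered outcome and the fact that the reaction was still open at later visits are all recorded. Sending an ISR with only ongoing PTs to 'unknown' discards what is known about it.

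At stake is the description of how long ISRs last. They are an event of interest in Protocol 8.4, and Protocol 4.5 names them as the exception to the absence of dose-related safety signals.

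**Working it through.** The plan states no figure on this point, and the primary analysis is descriptive ("No statistical model will be applied for the primary endpoints"). The check is therefore to apply the stated rule to test cases.

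**Inputs.** Grouping, worst case, exclusion and the 'unknown' row are from SAP 2.7.1.2; the treatment of ongoing events is from SAP 5.2.2; the need for an end date is from SAP 2.1.1. Assumptions: an ongoing record has a missing resolution time; '24 hours' means up to 24 hours; an ongoing record in the test cases is still open at 28 days.

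**Rule as written.** Remove records with no resolution time, take the longest category among the rest, and use 'unknown' if none remain.

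**Alternative.** Keep an ongoing record at the time already observed, with a flag.

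| ISR in one dosing window | Rule as written | Ongoing records kept |
|---|---|---|
| A. One PT, ongoing | unknown | > 72 hours, ongoing |
| B. Two PTs: resolved at 20 h; ongoing | 24 hours | > 72 hours, ongoing |
| C. Two PTs, both ongoing | unknown | > 72 hours, ongoing |
| D. Two PTs, resolved at 20 h and 96 h | > 72 hours | > 72 hours |
| E. Two PTs: resolved at 96 h; ongoing | > 72 hours | > 72 hours, ongoing |
| F. One PT, resolved at 200 h | > 72 hours | > 72 hours |

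B is the fault: an unresolved reaction in the most favourable category. A and C lose known information but stay visible as 'unknown'. D and F show that slow reactions with an end date are classified correctly. In E the category is unchanged, but nothing shows that a component is still open.

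**Size, by assumption only.** The documents do not say how often an ISR has several PTs or how often a PT is ongoing. Let m be the share of ISRs with two PTs (the rest have one), and q the probability that a record is ongoing, independently. Take m from 0.1 to 0.5 and q from 0.01 to 0.10.

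- One PT resolved and one ongoing, so that only the resolved time is used: m × 2q(1 − q). Lowest: 0.1 × 2 × 0.01 × 0.99 = 0.002. Highest: 0.5 × 2 × 0.10 × 0.90 = 0.090.
- All PTs ongoing, so 'unknown': (1 − m)q + mq². Lowest (m = 0.5, q = 0.01): 0.005 + 0.00005 = 0.005. Highest (m = 0.1, q = 0.10): 0.090 + 0.001 = 0.091.

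Per 20 ISRs this is 0.04 to 1.8 of the first kind and 0.1 to 1.8 of the second. The first count includes case E, where the category happens to be right.

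**Context.** Ligelizumab ISR rates in the asthma study quoted in Protocol 4.5 were 12.5% and 28.6%. If they carried over, 65 × 0.125 = 8.1 and 65 × 0.286 = 18.6, or about 8 to 19 subjects with an ISR.

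**The case against.** The strongest reply is that few records are affected and that nothing is hidden.

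- **Few ongoing ISRs.** Protocol 10.1.1 requires events to be followed to resolution or until judged permanent. The last visit is 16 weeks after the last dose, so in a completer an ISR that began soon after an injection and is still open at the end has lasted about that long or longer. Otherwise it takes early exit or lost data. Protocol 4.5 describes previous ISRs as reversible, apart from one medically significant case. This stands, and it is why the effect is probably small.
- **Visible elsewhere.** The Outcome summary and the by-subject display of adverse events still show unresolved ISRs. This also stands, but two tables that disagree about the same reaction remain a fault.
- **'Ongoing' is not called missing.** SAP 5.2.2 concerns date imputation and does not say how an ongoing event enters the ISR table. That is correct. Without an end date, however, the SAP offers no other way to assign a resolution time, so the gap needs closing on either reading.
- **No decision depends on it.** The table is descriptive, and a single-arm, single-dose trial cannot assess a dose trend. This stands and limits the importance of the point.

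A reader might infer that the slowest reactions drop out of the table altogether. They do not: exclusion is per summary, an ISR with no usable record gets the 'unknown' row, and slow reactions with an end date stay in '> 72 hours'.

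A reader might also see a contradiction with SAP 2.5.2, where "missing severity will be assumed to be severe in the summary table". That rule is written for the table of adverse events by maximum severity. The ISR severity table has its own rule and an 'unknown' row, so the difference is a choice, not an error.

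**Conclusion.** The point holds in a limited form. When an ISR has both resolved and ongoing PTs, SAP 2.7.1.2 bases its resolution time on the resolved PTs alone, which can place it in '24 hours'. When all its PTs are ongoing, it becomes 'unknown' even if known to exceed 72 hours. The bias runs only toward shorter resolution and goes against the SAP's own worst-case principle.

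This rests on reading an ongoing event as having a missing resolution time. Only records that are ongoing or lack an end year are touched, and the '24 hours' misreport needs at least two PTs in one window. The frequency is unknown and probably low; the 0.2% to 9.0% range is illustrative. Counts of treatment-emergent events, exposure-adjusted rates, ISR incidence, time to first ISR and the Outcome summary are unaffected.

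Two further inferences are not supported:

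- **Size.** The 5.2% in Protocol 4.5 is a placebo rate, so it is no lower bound for a trial in which everyone receives ligelizumab. The lowest ligelizumab rate there is 12.5%.
- **Category limits.** A duration of exactly 72 hours is not ambiguous, because the top category is strictly above 72. The shared limits at 24 and 48 hours are a missing detail and not part of this point.

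**What to change.** In SAP 2.7.1.2, state that a PT record that is ongoing or not recovered/not resolved takes part in the worst-case choice for time to resolution as the worst level. Either add a 'not resolved/ongoing' level, or assign '> 72 hours' when the reaction was observed beyond 72 hours. The added level is simpler, because it needs no rule for reactions last observed before 72 hours, and it agrees with the Outcome summary. Keep 'unknown' for ISRs whose records truly lack the information.

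The cost is a sentence or two of SAP text and a small programming change, with no new data. The resolution table may look slightly less favourable.
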